
### Procedures

**NOTE - PANDEMIC-RELATED CHANGES:** As of August 2020, the entire AD-MIL study is being conducted virtually due to the COVID-19 pandemic. We have provided more information on how we are adapting to these times.

### *Recruitment*

Veterans will be recruited and treated at VA sites in Minneapolis, MN, San Diego, CA (Oceanside CBOC), San Francisco, CA, and Waco, TX (CTVHCS). Co-Investigators (Co-Is) at these study sites have successfully resolved operational obstacles and challenges to implementing clinical trials in their respective settings. Referrals for clinical studies have been nurtured through each Co-I's role as a clinician and PTSD expert. Co-Is will (a) provide materials describing the nature of the study and the target populations sought, distributing said materials via formal (e.g., staff meetings) and informal (e.g., bulletin boards) channels; (b) attend clinical staff meetings; (c) give talks to describe various treatments in staff grand rounds and other contexts (e.g., to trainees); (d) provide feedback to staff about referred patients.

**COVID-19 changes:** There will be no face-to-face recruitment. Instead, sites will recruit at Virtual Clinic Staff meetings rather than in person.

### *Consent and Pre-Eligibility Screening*

A trained research assistant (RA) at each treatment site will pre-screen interested veterans for basic eligibility requirements (see above for inclusion criteria and exclusion criteria) and schedule consent and eligibility/baseline assessment appointments with site RA and an independent evaluator (IE). Research personnel at the coordinating site (i.e., Boston) and all study sites (i.e., Minneapolis, San Diego, San Francisco, and Central Texas) will serve as IEs. However, to assure independence, in the case of dual roles (IE and study therapist), IEs will not perform any assessments with veterans who they will treat or have treated. At the consent and eligibility/baseline visit, the RA will first obtain in-person, written informed consent and HIPAA authorization for study participation and recording of assessments and treatment sessions, and collect demographic information. Veterans will be informed about all potential study risks during the informed consent process, including limits to confidentiality. They will be informed that they can refuse to answer any question or terminate their assessments at any time if they so desire.

Also at the eligibility/baseline visit, Veterans will complete the PTSD diagnostic assessment by telephone with the IE. The study site RA will ask the veteran to read the IE site's informed consent form for the telephone evaluation while the IE is called on the telephone. The IE will verbally instruct participant to confirm that the participant has signed, initialed, and dated in the appropriate places in the written informed consent for the IE's site and in the HIPPA authorization form. The IE will ask whether the veteran agrees to be audio recorded. If the veteran consents, the IE will start the audio recorder and complete a telephone consent form that confirms oral consent of participant. If the veteran consents, the IE will sign and date a telephone consent form stating that the IE received verbal consent for evaluation and recording.

The IE will administer the LEC to measure exposure to various traumatic events; veterans will also be asked to clarify whether each event that they endorse happened during military service, civilian life, or both. Next, the IE will begin the CAPS-5 assessment by asking veterans to report their worst or most currently distressing military related experience. To account for trauma-types in post-hoc analyses, we will use a procedure to type index events that are used in the STRONG STAR consortium and the Consortium to Alleviate PTSD (CAP; [name] is the assessment core director of each). This entails patients indicating whether any of the following applies to the event: (1) during the event they thought they or someone else could be seriously injured or killed (threat-based); (2) the event entailed the loss of a friend or unit member (loss); (3) they experienced the sights, sounds, and smells of dead or badly wounded people (the grotesque aftermath of battle, an MI); or (4) the event entailed something the veteran did or failed to do or entailed something that someone else did or failed to do (MI). The participant is then asked to indicate which one of these aspects was the worst part of the event. If the participant is unable to choose only one of these, s/he will be asked to rank the worst parts of the event from most to least distressing. The IE will then continue the assessment with the CAPS-5, select modules of the MINI, and the Mental Health Service History form.

The site RAs will emphasize to veterans that their therapists will not see the CAPS-5 results. As with any psychotherapy, increased distress is expected in response to discussing symptoms during assessment and therapy procedures. During evaluation and treatment, participants will have the support of experienced clinicians and be provided with emergency contact information.

Following the phone call with the IE, the site RA will administer all self-report measures. Baseline measures will be completed the same day as screening/eligibility regardless of whether the individual is preliminarily eligible based on screening. If a participant waits for a month or more before starting therapy after the baseline session, the baseline measures will be re-administered.

**COVID-19 Changes:** All communication with participants is being conducted either via a HIPAA-compliant videoconferencing platform or over the phone.

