## METHOD

### Overview

We plan to conduct a multi-site randomized controlled trial of AD-MIL, comparing it to PCT (Frost et al., 2014). Study recruitment and treatment will occur off-site at four VA partnering sites: Minneapolis, MN, San Diego, CA (Oceanside CBOC), San Francisco, CA, and Waco, TX (Center for Returning Veterans Center of Excellence at the Central Texas Veterans Healthcare System; CTVHCS). VA Boston's research roles are to: (1) conduct weekly and PRN oversight and supervision meetings to problem-solve recruitment, treatment delivery, patient compliance, and data collection issues; (2) conduct blinded phone interviews to diagnose PTSD using the Clinician-Administered PTSD Scale for DSM-5 (CAPS-5) before treatment and at three time points after treatment; (3) manage and analyze de-identified data sets; and (4) help prepare manuscripts and reports.

The trial will follow the consensus recommendations for clinical trials in the VA (VA-ORD, 2008): (1) clearly defined target symptoms: Functional and clinical outcomes will be operationalized; (2) reliable and valid measures: Assessment tools are selected for their content relevance and psychometric properties; (3) use of blind evaluators of outcome: The evaluator will be independent and blind to treatment condition. The assessor will remind participants to help maintain their blind; (4) assessor training: The independent evaluator (IE) will be carefully trained to criteria and monitored on an ongoing basis; (5) manualized, replicable, specific treatment programs; (6) unbiased assignment to treatment arms and (7) treatment adherence: Sessions will be recorded, and a random percentage will be used to assess treatment integrity. Adherence to the therapy manuals will be monitored by senior supervisors. We will follow the CONSORT guidelines for randomization and participant tracking.

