#### *Treatment Training, Supervision, and Fidelity Monitoring*

Therapists with Ph.D.s in clinical or counseling psychology and VA internship experiences treating veterans with PTSD will be trained to deliver AD-MIL or PCT (not both).

Training and supervision of AD-MIL and PCT trial cases will be provided by Drs. [name] and [name]. [name] developed AD for the Marine Corps trial and has spearheaded the extension of AD principles in the development of AD-MIL. [name] has extensive expertise in the conduct of PCT. Training will involve a review of the respective manuals and supporting materials, intensive supervision of trial cases, and weekly group and one-on-one phone supervision with [name] for AD-MIL and [name] for PCT). Drs. [name] and [name] will review audio recording of treatment sessions (all treatment session will be audiotaped) as needed to facilitate their supervisory roles. Selected sessions will be securely transferred to an approved and secure drive within the VA firewall to Drs. [name] and [name].

Treatment fidelity monitoring will be conducted by Drs. [name] and [name]. [name] was instrumental in the development of AD for the Marine Corps trial and has served as a consultant in the extension of AD principles in the development of AD-MIL. [name] has extensive expertise in the conduct of PCT. Fidelity monitoring will be executed via the following procedure: 100% of a patient's first two sessions will be selected for review, 50% of next two, 20% of next five and 10% thereafter. After ten subjects, the therapist will discuss with the site RA which sessions to send for review to total 10% of caseload. Selected sessions will be securely transferred to an approved and secure drive within the VA firewall to [name]. Selected sessions will be securely transferred to [name] via encrypted email (see attached Data Use Agreement).

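### Study therapists may conduct follow-up CAPS-5 interviews with veterans they do not treat, so the promised evaluator blind is not assured for those ratings

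*Combined protocol and SAP*

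**What the plan says.** The Overview commits the trial to blinded outcome assessment: "The evaluator will be independent and blind to treatment condition". Among the tasks of the Boston site, which does not treat participants, it lists this one: "conduct blinded phone interviews to diagnose PTSD using the Clinician-Administered PTSD Scale for DSM-5 (CAPS-5) before treatment and at three time points after treatment". One measure is named to keep the blind: "The assessor will remind participants to help maintain their blind".

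Consent and Pre-Eligibility Screening describes a wider pool. IEs are drawn from "Research personnel at the coordinating site (i.e., Boston) and all study sites", and the section foresees that some will also be study therapists. For those people the rule is: "in the case of dual roles (IE and study therapist), IEs will not perform any assessments with veterans who they will treat or have treated". The section gives independence, not blinding, as the purpose of this rule.

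Treatment Training, Supervision, and Fidelity Monitoring says that therapists "will be trained to deliver AD-MIL or PCT (not both"), and that training includes "intensive supervision of trial cases" as well as "weekly group and one-on-one phone supervision with [name] for AD-MIL and [name] for PCT".

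**The concern.** The dual-role rule stops therapists from rating their own patients. It does not stop a therapist from rating a veteran whose allocation that therapist already knows. A therapist who works in one arm and joins that arm's weekly supervision may hear about colleagues' patients, and any trial case raised there is in that arm. The same person may then be the IE at that veteran's follow-up.

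This matters because the CAPS-5 is the interviewer-rated outcome in the trial's hypotheses. The SDS and PCL-5 are self-reported by veterans who know which therapy they are receiving, so the CAPS-5 is where evaluator blinding does most of its work. If the plan is followed as written, the report could describe CAPS-5 assessment as blinded although some interviews were done by people who deliver one of the two compared treatments and may have known the arm.

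**Working it through.** There is no figure to reproduce. The check sets the sections side by side.

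1. **Who may rate at follow-up.** The Overview gives the CAPS-5 interviews to Boston. Consent and Pre-Eligibility Screening opens the IE role to all treating sites and to therapists. Follow-Up Assessments says only that an IE conducts the CAPS-5 by phone for every participant. It adds no stricter rule after randomisation, and the dual-role rule is worded to cover assessments of any kind. Therapist-IEs are therefore permitted at follow-up.

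2. **What the rule excludes.** For a given therapist it excludes that therapist's own past or future patients. Every other participant remains open to them, including colleagues' patients in the same arm.

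3. **What a therapist may know.** Therapists belong to one arm, and the two arms have different supervisors. A case discussed in a single-arm group reveals its allocation to everyone present. The text lists supervision of trial cases and the weekly group and individual calls as items in one sentence. It does not say whether patients are identifiable in the group call.

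4. **What stands in the way.** The assessor's reminder guards against disclosure by the veteran, not against what the assessor has heard from colleagues. Assessor Training and Adherence provides for audio review of a random 10% of assessments, but as a check on standardised administration. No section masks cases in supervision, bars therapists from rating veterans in their own arm or at their own site, or checks whether IEs remained blind.

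5. **Which outcomes are exposed.** CAPS-5 severity and PTSD caseness after randomisation, both under Hypothesis B.4. The SDS and PCL-5 are completed by the veteran. The eligibility CAPS-5 comes before assignment, so there is no allocation to know.

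6. **Size.** The number of affected ratings would be:

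   follow-up CAPS-5 interviews × share done by therapist-IEs × share of those in which the allocation was known.

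   The documents give neither share. The bias in the arm comparison would also need the mean rating shift and its balance between arms, since therapist-IEs from the two arms could partly offset each other. None of these is given, so no estimate is possible.

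**The case against.** The strongest reply is that a permission is not a practice. The documents do not say how many IEs are therapists, whether any of them do follow-ups, whether they rate at their own site, or whether supervision identifies patients. Several sections describe interviewing across sites: the veteran reads a consent form from the IE's site, Boston assessors interview remotely, and the reporting rules provide for a Boston IE who learns of an adverse event. Boston and other non-therapist IEs are outside this route. All of this stands, and it limits the claim to a blind that is unprotected.

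Four stronger readings are tempting, and the documents do not support them:

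- **The blind cannot hold.** This would need known frequencies of dual roles and of identifiable case discussion. Neither is stated.
- **A veteran never mentioned in one arm's supervision must be in the other arm.** That inference works well only if therapists rate at their own site and the group covers every case there. The text says neither.
- **Ratings could shift by 8 points without being noticed.** A reader might take the 2-point tolerance on each of four symptom clusters and compute 4 × 2 = 8. That tolerance certifies assessors in training, and a match also requires agreement on diagnosis. It does not set an allowance for trial ratings, and the audio review is a further, partial check on drift.
- **The primary result is compromised.** The SDS is self-reported and is not reached by this route. Hypothesis B.4 also has a self-reported severity measure, the PCL-5.

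What remains is that no section closes the route.

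**Conclusion.** The point holds in limited form. The plan promises a blind evaluator, permits therapists to be evaluators for veterans they do not treat, and places those therapists in single-arm supervision without any barrier to learning allocation. The blind is therefore not assured for post-randomisation CAPS-5 severity and PTSD caseness. This rests on the permission in the text and on the assumption, plausible but unstated, that trial cases can be recognised when discussed in group supervision. The extent and direction of any bias are unknown. It is a weakness in a secondary, clinician-rated outcome that is cheap to repair, and not a reason to doubt the primary analysis.

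**What to change.** Amend the dual-role sentence in Consent and Pre-Eligibility Screening so that no one who delivers, or attends case supervision for, either study treatment conducts a CAPS-5 with any participant after randomisation. Assign these interviews to the Boston IEs described in the Overview, or to other existing IEs who are not therapists. Therapist-IEs may continue with pre-randomisation interviews, subject to the present own-patient rule.

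For interviews already done, flag those conducted by a therapist-IE and repeat the CAPS-5 severity and caseness analyses without them as a sensitivity analysis. In the mixed model the removed ratings are treated as missing; the chi-square test for caseness is run on the remaining participants. This requires that the interviewer be identifiable for each CAPS-5, which the documents do not state outright.

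The cost is one amended sentence, one scheduling rule and one extra analysis. Location should be little obstacle, because the follow-up CAPS-5 is already done by phone and assessors may work from home. The downside is that follow-up calls fall on fewer IEs. A reader might assume that no new staff are needed because the Overview already lists these calls under Boston, but IE capacity is not stated. If capacity is limited, the flag and the sensitivity analysis can still be done at almost no cost.

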#### *Follow-Up Assessments*

Follow-up assessments will be completed 3 months, 6 months, and 9 months after the first treatment session, or, if no treatment sessions were attended or a participant terminated therapy early, 3 months, 6 months and 9 months after the baseline assessment. As part of these follow-up assessments, all participants will complete CAPS-5 assessments by phone with an IE. In most instances, these calls will occur while the participant is in person at their local VA (i.e., Minneapolis, San Diego, San Francisco, or Central Texas). In cases where a participant is unable to attend a follow-up assessment at their local VA in person, we will offer participants the opportunity to complete the CAPS-5 assessment by phone from their home or another non-VA location. In instances where the participant is not at their local VA, IEs will conduct a thorough risk assessment during the call, and follow thoroughly defined procedures for risk management and safety planning when indicated (see “Follow-up Risk Assessment Phone Script” attached).

**COVID-19 aim:** Participants randomized between 12/31/2020 and 5/31/2021 will complete follow-up assessments 3 months and 6 months after the first treatment session, or, if no treatment sessions were attended or a participant terminated therapy early, 3 months and 6 months after the baseline assessment. Participants randomized between 6/1/2020 and 8/31/2021 will complete a follow-up assessment 3 months after the first treatment session, or, if no treatment sessions were attended or a participant terminated therapy early, 3 months after the baseline assessment.

**COVID-19 Changes:** All communication with participants is being conducted either via a HIPAA-compliant videoconferencing platform or over the phone.

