#### **A: Functional and behavioral change hypotheses:**

- A.1.** Immediately post-treatment, 3-, and 6-months post-treatment, veterans with PTSD randomized to AD-MIL will have greater reductions in social, educational, and occupational disability
- A.2.** COVID-19 aim. In the extended time period for the trial, at the post-treatment, or post-treatment and 3-months post-treatment intervals (depending on when the participant was randomized), veterans with PTSD randomized to AD-MIL will have greater reductions in social, educational and occupational disability

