### **ANALYSES**

**Inferential analyses.** The longitudinal and clustered nature of the design produces a multilevel or nested data structure (Raudenbush & Bryk, 2002), with a likelihood of between-subject variability in treatment trajectory over time (e.g. random slopes). In this study, veterans and therapists are nested (clustered) within performance sites. The lower level (level-1) data consists of the repeated measures for each individual at each assessment. Level-1 data is nested within upper level (level-2) person-level variables (e.g., study site).

Using the most up to date statistical software such as SAS 9.4 and R/R Studio, we will explore the change trajectory of endpoints over the course of pre-treatment, during-treatment, and post-treatment time intervals. Specifically, we will use the linear mixed model regression framework to assess the differential treatment effects of endpoint symptom burden over time. We will examine observed measurement scores and specify linear mixed models that best fit the time-change trends (e.g. linear, piecewise). We will test for the presence of random variation, such as between-site cluster effects and between-subject random slopes of treatment effect. We will determine the best fit linear mixed effects model as a combination of most appropriate representation of time and empirically-evidenced random and fixed effects.

The linear mixed effects models will incorporate clinically relevant time-invariant and time-varying predictors and will use Maximum Likelihood Estimation to produce estimates that are unbiased in the presence of random missingness and dropout. They will provide an Intent-To-Treat (ITT) analysis that will incorporate all available data. Per-protocol and “completer” subset analyses will be performed under the same paradigm. Additionally, a subset of subjects whom began therapy during the COVID-19 pandemic will be identified and analyzed separately; they comprise subjects which began therapy following December 31st, 2020. The tenability of the “At-Random” missingness assumption will be assessed and a sensitivity analysis of the results will be conducted to determine robustness of the inferences.

**Aim I:** Randomized controlled trial of AD-E, comparing it to PCT:

**Hypotheses 1 and 2:** Veterans in the AD-E arm will have a steeper downward slope in SDS (primary endpoint). Identical calculations will be performed with the B-IPF and DRRI-2 Post-Deployment Social Support measure.

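### The one-visit COVID-19 window, dated from 6/1/2020, contains the whole two-visit window and starts seven months before the COVID-19 subset, so follow-up schedules conflict; the year is probably wrong

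*Combined protocol and SAP*

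**What the plan says.** The default rule under Follow-Up Assessments is: "Follow-up assessments will be completed 3 months, 6 months, and 9 months after the first treatment session". The clock runs from baseline instead for veterans who attend no sessions or stop therapy early.

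Under the COVID-19 aim label, the same section adds two rules keyed to randomisation date:

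- "Participants randomized between 12/31/2020 and 5/31/2021 will complete follow-up assessments 3 months and 6 months after the first treatment session"
- "Participants randomized between 6/1/2020 and 8/31/2021 will complete a follow-up assessment 3 months after the first treatment session"

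Three other places bear on these dates:

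- **Hypothesis A.1 (Objectives)** names three time points: "Immediately post-treatment, 3-, and 6-months post-treatment, veterans with PTSD randomized to AD-MIL will have greater reductions in social, educational, and occupational disability".
- **Hypothesis A.2 (Objectives)**, the COVID-19 aim, is placed "In the extended time period for the trial". Its outcomes are taken "at the post-treatment, or post-treatment and 3-months post-treatment intervals (depending on when the participant was randomized").
- **Analyses** sets apart a COVID-19 subset: "they comprise subjects which began therapy following December 31", 2020. This cut-off uses the start of therapy, not randomisation.

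No section says which schedule applies to a veteran who meets more than one rule, and none explains the 6/1/2020 date.

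**The concern.** A rule that assigns visits by date works only if each date leads to one schedule. Here a veteran randomised in March 2021 meets both COVID-19 sentences, one calling for visits at 3 and 6 months and the other for a single visit at 3 months. A veteran randomised in September 2020 who began therapy that autumn is outside the COVID-19 subset under Analyses, yet falls inside a COVID-19 window with one visit, while the default rule still calls for three.

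At stake are the later time points. In the March 2021 case, the 6-month visit is the only source of that veteran's data for the part of A.2 set three months after treatment. In the September 2020 case, the 6- and 9-month visits supply the last two time points of A.1. Four treatment sites and the central evaluators schedule from this text, and a visit not made in its window cannot be recovered afterwards.

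**Working it through.** The plan states no figure for this point, so the check is calendar arithmetic on its own dates. Day counts are inclusive: end date minus start date, plus 1.

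**1. The windows (Follow-Up Assessments)**

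- Two-visit window, 12/31/2020 to 5/31/2021: 152 days.
- One-visit window, 6/1/2020 to 8/31/2021: 457 days.

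**2. The overlap**

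The later of the two starts is 12/31/2020 and the earlier of the two ends is 5/31/2021. The overlap is therefore 152 days, which is 152/152 = 100% of the two-visit window.

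**3. The one-visit window split by which rules apply**

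| Randomised | Days | Rules met as written |
|---|---|---|
| 6/1/2020 to 12/30/2020 | 213 | default (3, 6, 9 months) and one-visit (3 months) |
| 12/31/2020 to 5/31/2021 | 152 | two-visit (3, 6 months) and one-visit (3 months) |
| 6/1/2021 to 8/31/2021 | 92 | one-visit is the only COVID-19 rule |

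The parts add up: 213 + 152 + 92 = 457. Conflicting rules cover 213 + 152 = 365 of the 457 days.

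**4. What the visits mean for the hypotheses**

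Treatment is 12 weekly sessions (Treatment Arms), about 3 months. Visits at 3, 6 and 9 months after the first session therefore fall at roughly 0, 3 and 6 months after treatment, which are the A.1 time points. Applied literally, the one-visit sentence drops the second and third of these for the first row of the table, and the second for the second row.

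**5. Test of a wrong year**

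Suppose the one-visit window began on 6/1/2021.

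- The windows become 152 and 92 days, with an overlap of 0 days and a gap of 0 days (5/31/2021 is followed by 6/1/2021).
- Counting from randomisation as a stand-in for the first session, the last visit is 5/31/2021 + 6 months = 11/30/2021 in one window and 8/31/2021 + 3 months = 11/30/2021 in the other.
- Nobody randomised before 12/31/2020 is affected.

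On the same count, a veteran randomised on 12/30/2020 reaches 9 months on 9/30/2021, before 11/30/2021. The calendar gives no reason to shorten follow-up for veterans randomised in 2020.

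**6. Randomisation date against therapy start**

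A veteran randomised in late December 2020, before 12/31, who starts therapy in January 2021 is outside the two-visit window but inside the COVID-19 subset under Analyses. Correcting the year alone does not remove this mismatch.

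**The case against.** The best reply is that this is a slip any careful reader would see through. The one-visit sentence sits under the COVID-19 aim label, A.2 places that aim in the trial's extension, and Analyses confines the subset to therapy begun after 2020. The default rule stays in the same section. The narrower two-visit sentence would have no effect if the broader one governed, so a sensible site would follow the narrower one. Much of this stands. It makes the intent fairly clear, but it does not make the operative text consistent, and no precedence rule is written down.

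Three stronger readings are tempting and should not be drawn:

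- **That main-trial veterans lose their later visits.** The documents give those randomised from 6/1/2020 to 12/30/2020 two conflicting schedules, not a certain loss. Also, only the one-visit window reaches back to 6/1/2020; the two-visit window does not.
- **That the primary comparison is undermined.** Sample Size powers each hypothesis at 3 months and calls analyses up to 6 months post-treatment exploratory. The 9-month visit is therefore exploratory. The 6-month visit would carry the powered comparison only if 3 months means after treatment, which that section does not make clear. Both COVID-19 rules keep the 3-month visit, and A.2 accepts post-treatment data alone for some veterans. The planned mixed models use all available data, so earlier observations would still count; the cost would be precision at later time points.
- **That the day counts measure lost veterans or lost power.** They count calendar days. The documents give no accrual by date.

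**Conclusion.** The date rules in Follow-Up Assessments are inconsistent as written and need correction, because they decide which follow-up visits take place. All 152 days of the two-visit window carry two COVID-19 schedules, and the 213 days before it carry both the default schedule and a 3-month-only schedule. The day counts rest on the printed dates alone.

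The harm is conditional. If a site follows the one-visit sentence literally, the A.1 visits at 3 and 6 months post-treatment (the latter exploratory), or the part of A.2 at 3 months post-treatment, would not be collected for the veterans concerned. The number of veterans cannot be computed.

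A wrong year is the probable explanation. It rests on the exact fit of the windows and their common end on 11/30/2021, which assumes that visits are counted from randomisation. A.2 and Analyses are consistent with it but do not prove it: A.2 gives no dates, and Analyses gives a single cut-off based on therapy start. The sponsor has to confirm the intended date.

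**What to change.** In Follow-Up Assessments, the sponsor should:

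1. Confirm and correct the start of the one-visit window so that the two COVID-19 windows do not overlap. A start of 6/1/2021 would make them consecutive.
2. State that veterans randomised before the COVID-19 window keep the default 3-, 6- and 9-month visits.
3. Reconcile the randomisation-date rule with the therapy-start cut-off under Analyses, so that a veteran who straddles the end of 2020 is classified in one way for both visits and analysis.
4. Notify the sites and the evaluators.

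The cost is one corrected date, one or two clarifying sentences and a note to sites. It adds no visits beyond those already planned for the main trial and the COVID-19 aim.
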